The protocol as described includes the entire subject set, which allow for comparisons between obese girls with and without PCOS. OGTT with an oral tracer will be conducted in all subjects. The specific points that are to be evaluated are listed below:

- 1) OGTT with glycerol tracers
 - a. Purpose: Develop an oral stimulus model to assess hepatic substrate flux
 - i. Question 1. Is 6.5 hours post oral load long enough to model hepatic and adipose insulin sensitivity?
 1. Rationale: In our current study (14-0542), we have found that 6 hours are required for metabolites to return to normal, we do not anticipate this to change greatly with the addition of the glycerol tracer.
 2. Measurement. Serum glucose and insulin will be measured post-glucose load for 6.5 hours in the first 6 subjects. If 6.5 hours post glucose values are within 20 mg/dL for glucose and 20 IU/mL for insulin relative to baseline values, 6.5 hours will be considered sufficient.
- 2) Measurement of Hepatic Substrate flux in youth.
 - a. Purpose: Optimize a model to asses hepatic substrate flux in youth looking at shifts from pentose phosphate pathway (PEP), TCA cycle and fatty acid synthesis
 - i. Rational: utilizing an oral glycerol model with NMR isotopomer analysis is a newer technique. It has not been validated in youth.
 - ii. Measurement: NMR isotopomer analysis with pathway flux calculations and modeling
 - iii. Revision plan if model not correct: 1) increase the amount of tracer given 2) increase the frequency of blood draws in the later sampling period.

Overall Project Limitations:

- 1) Subject recruitment is always a potential concern, but is minimized by a streamlined recruitment system and experience with this population; the previous, more intensive study is well tolerated in youth and enrolled faster than projected. In addition, we had >100 new PCOS referrals to our pediatric endocrinology department in 2013 alone, and the PI has a clinic specifically for girls with PCOS.
- 2) Subject drop-out: We expect reasonably good completion rates due to the non-invasive nature of the two study visits and our low dropout rate in our previous studies in control and PCOS adolescents using similar procedures.

V. Data Management and Security Plan

Data Entry

Data will be entered from paper forms. Once forms are completed, verified and corrected for inconsistencies, they will be manually entered at our site using a computerized data management system (Redcap).

Edit Checks

Computerized data validation routines will be used to enhance data quality and verify the accuracy of data within predefined value ranges. These checks include, but are not limited to: (a) initial screening of data, using logic and range checks built into data entry screens; (b) cross-form functional and consistency checks; and (c) edits assessing the serial integrity of data.

Disaster Recovery

Routine data backup will occur on data in conjunction with the Children's Hospital secure server and Redcaps.

Security and Confidentiality

All hard copy forms will be de-identified with a study number and filed in a locked cabinet, to which only the investigators will have access. Standard protection against computer hackers is implemented. Recovery from natural disasters (water, fire, or electrical) can occur through the ability to reconstruct both the database management system and the data from nightly backups.

VI. Data and Safety Monitoring Plan

The principal investigator and study coordinator will monitor the protocol and the safety of the research subjects. The PI will review all laboratory data and report any abnormal values to the patient and guardian and instruct the subject to follow-up with their PCP. If an abnormal result from a research procedure exists, the PI will notify the family and their PCP and refer the participant to the appropriate clinic for further evaluation. The PI may also share research results in a reasonable and prudent manner with appropriate medical professionals if the participant was seriously injured as a result of a procedure or if follow-up of the result of the procedure is in the best interest of the participant's health as determined by a medical professional. If immediate medical follow-up of participant required, the PI will share the research results via EPIC when clinically relevant. The PI will report adverse events, and any decision to suspend or halt the protocol to CTRC and COMIRB immediately. The PI will also prepare a written report for the yearly continuing review required by COMIRB and the CTRC. There are no other entities that require notification about this protocol.

No protected health information will be collected until the appropriate HIPAA forms are completed. The protected health information that will be collected will include: Name and phone number, demographic information (DOB, sex, ethnicity, address, etc.), diagnosis (es), history and physical, laboratory or tissue studies, radiology studies, procedure results, survey/questionnaire results, research visit records, and portions of previous Medical Records that are relevant to this study. This information will be accessible only by the study investigators, Federal agencies overseeing human subject research, the Colorado Multiple Institutional Review Board, regulatory officials from the institution where the research is being conducted to monitor safety and compliance with policies.

A. Adverse Events (AE)

The OGTT is a standard procedure used in a large number of research studies and settings. Adverse events are uncommon when the procedure is done by experienced personnel in an appropriate setting.

1. Adverse Event Definition

For the purposes of this study, an Adverse Event (AE) is defined as any significantly abnormal physical finding identified on examination and any significantly abnormal laboratory result obtained on the patient between visits or at the time of the visit. Questions answered YES and any new abnormal physical findings are pursued by the study staff in order to determine the seriousness of the event and the need for further evaluation, follow-up, or referral. If follow-up or referral of abnormal research results or procedure is required, the PI will place a referral in EPIC, update the PCP on patient condition and reason for referral and contact family to discuss follow-up treatment options.

a) Adverse Event Reporting

AEs are reported on a standard form that is completed by the study staff at each regular follow-up visit and phone interview. Adverse events reported or ascertained between clinic visits are captured and reported at the time of the next scheduled visit.

Pre-existing conditions (that is, conditions present prior to study enrollment) are not considered or recorded as AEs or SAEs unless the condition worsens in intensity or frequency after enrollment. Likewise, continuing adverse events are not reported as AEs at subsequent visits unless they increase in severity or frequency between the visits, they result in criteria for an SAE, and/or they resolve between visits.

B. Serious Adverse Events (SAE)

1. Serious Adverse Event Definition

Events are divided into those that are not serious (AE) and those that are serious (SAE). The distinction between an SAE and an AE is a regulatory definition established by the FDA, not a clinical definition. The definition of SAE is not always related to clinical severity of the event. For the purposes of this study an AE is considered a Serious (SAE) when it satisfies any one of the following criteria:

- The event results in an inpatient hospitalization (any overnight stay associated with an admission).
- The event results in the prolongation of a hospital stay.
- The event results in permanent or severe disability.
- The event results in death.
- The event is life-threatening.
- Treatment is required to prevent a serious event.

There have been no SAE's in the research groups experience in the Pediatric CTRC. We do not anticipate encountering SAE's; however, we have identified the following as possible SAE's for the purposes of monitoring:

- Infection related to blood draw or IV placement

a) Serious Adverse Event Reporting

Study patients are instructed to contact the clinic with any serious adverse event meeting the above criteria. Each SAE is recorded on the study form and the PI is informed as soon as possible after they occur and preferably within 24 hours of the notification of the clinic staff. This notification should occur even if data are incomplete. Additional data and follow-up information are documented and sent subsequently as an update to the original report. The PI immediately forwards SAE reports to the COMIRB and any other required institutional monitoring committee.

C. Subject Discontinuation Criteria

If a subject experiences any of the following, the subject will be withdrawn from the study.

1. Inability to complete study procedures
2. Abnormal screening labs (LFT's >150 IU, HbA1C>6.4%, Hg <10 mg/dL)
3. Subject becomes pregnant during study

D. Protocol Stopping Criteria

If one or more subjects experience any of the SAE's listed above, the PI will consult with the study staff prior to continuing study visits with subjects. The PI and RSA will consult about the significance of the SAE's and make a recommendation about subject continuation in the study.

VII. Data Analysis Plan:

Overall Project Statistical Plan:

Power calculation: The primary outcome is hepatic substrate flux pathway percentages measured as PEP, TCA and TG synthesis pathways. Power analysis is based on publications utilizing similar methods, with the Primary Aim of understanding differences in hepatic metabolism in obese girls with PCOS who either have or do not have hepatic steatosis. The reference manuscript included 13 men without HS, and 6 men with HS⁵⁰. They found that during hyper-insulinemia, glycerol related gluconeogenesis was increased, as was the PEP cycle in individuals with HS compared to those without. Utilizing the PEP value, from this paper, the difference between the group means is 3 μ mol.min.kg FFM, and the standard deviation is 2 μ mol.min.kg FFM. Differences between the two primary groups (PCOS, controls) will be assessed with a t test or for non-normally distributed data a non-parametric test such as Mann-Whitney U. With 15 untreated PCOS with HS and 15 untreated PCOS without HS, we would have a power of 0.97 to detect an alpha of 0.05. Since the reference population is men who have more uniform hormone profiles, I am choosing to be overpowered should the variability in our population be greater. As the measurement is in kg of fat free mass, we will not have to do adjustments with BMI or weight. However, as African Americans are less likely to have HS, and Hispanics more likely to have HS, if ethnicity percentages are different between groups, we will need to adjust for ethnicity in our calculations.

Secondary Aims: a) For comparison of the PCOS to control groups, individuals will be matched in terms of HS status, so that the comparison is just between the hormonal state. I am assuming that there will be less of a difference between these groups, so with a difference of 2 Umol.min.kg FFM, and the standard deviation is 2, with 20 PCOS and 20 controls, we would have a power of 0.87 to detect a alpha of 0.05. b) For comparison of treatment with either metformin or OCP's, we will compare the untreated group to the treatments individually. We will not compare the two treatments to each other. I am assuming that there will be less of a difference between these groups, so with a difference of 2 Umol.min.kg FFM, and the standard deviation is 2, with 30 PCOS and 15 in a treatment group, we would have a power of 0.87 to detect a alpha of 0.05.

All measures will be adjusted for OSA status (yes/no) and/or severity of AHI.

Secondary outcomes include a Pearson correlation test of potentially related variables followed by targeted multiple regression to assess the relationship between hepatic fat and adipose IR, PEP, TCA, TG synthesis pathways.

Non-Isotope OGTT calculations: The Matsuda model of IR will be used but adapted for the 6.5 hour OGTT, and B-cell function [insulinogenic index ($\Delta I30/\Delta G30$) and ($\Delta C30/\Delta G30$) and disposition index ($1/I_{Fasting} \times \Delta I30/\Delta G30$) and ($1/C_{Fasting} \times \Delta C30/\Delta G30$) will be calculated^{38,49,51,52}.

Differences between groups will be evaluated with and without controlling for activity and sleep status.

Fitting glucose and glycerol concentrations curves: Using computed data points, glycerol and glucose concentrations will be fitted with an appropriate model. In control subjects, concentration typically shows 3 phases in OGTT ⁵³. Cubic polynomial, piecewise-linear, spline, and dynamic models have been used for fitting Ra in previous work^{54,55}. We will assume a cubic polynomial model; we will validate estimates obtained with the cubic polynomial model by computing comparable estimates using at least one other model form. In previous work comparing different models (piecewise-linear, cubic polynomial, dynamic), results have been relatively unaffected by choice of model. If we find that this is not the case for our data, then we would certainly consider the advantages of adopting a more complex approach, such as the state-space, for describing concentration changes.

Metabolomics data: Differences in targeted metabolic concentrations will be compared between groups, after appropriate cleaning of the data, as performed by the processing site. Changes in metabolites over time will be compared between groups, to determine the times that demonstrate the largest differences. Results will also be compared to isotopomer results, to see if a metabolomics endpoint can yield similar information to the isotopomer analysis.

Gut Microbiota: The microbiota profile is entirely exploratory, and will be related to status of hepatic steatosis and 2 hour glucose status of impaired glucose tolerance or not.

VIII. Summarize Knowledge to be Gained:

Overall Expected Results: We anticipate that we will determine which specific areas of hepatic metabolism are upregulated in girls with hepatic steatosis. This data would then provide the background evidence for future therapeutic trials. We will also refine this protocol and identify if metabolomics can be utilized to measure this type of hepatic energy flux.

Significance: Recent evidence in adults with PCOS indicates that 60-70% have NAFLD^{7,15}. Our data shows that > 45% of obese girls with PCOS have NAFLD, likely an underestimate due to exclusion criteria of T2D and weight >250 lbs in the previous protocols. The majority of NAFLD studies have focused on males, and none have been performed in multi-race cohorts of girls with PCOS, despite this high prevalence. NAFLD has been described as the primary driver of worsening metabolic syndrome and CVD in obesity across populations, and can progress to cirrhosis and liver failure^{5,6}. Thus, understanding the relative contributions of adipose and hepatic IR to NAFLD is critical to designing strategies to improve the long term health of these girls and reduce their risk of T2D, CVD and liver failure.

IX. References:

5. de Groot PC, Dekkers OM, Romijn JA, Dieben SW, Helmerhorst FM. PCOS, coronary heart disease, stroke and the influence of obesity: a systematic review and meta-analysis. *Human reproduction update* 2011;17:495-500.

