Title: Post-Prandial Liver Glucose Metabolism in Polycystic Ovarian Syndrome (PCOS) and understanding Standard of Care Medications

Version Date: 8/17/2017

NCT03041129

COMIRB Protocol

COLORADO MULTIPLE INSTITUTIONAL REVIEW BOARD
[name] [contact] [contact]

Project Title: Post-Prandial Liver Glucose Metabolism in Polycystic Ovarian Syndrome (PCOS) and understanding Standard of Care Medications

Version Date: 8/17/2017

Principal Investigator: [name] [name], PhD

I. Hypotheses and Specific Aims:

HYPOTHESIS:

Obese girls with hepatic steatosis (HS) will have hepatic glucose metabolism that is upregulated towards de novo lipogenesis (DNL) via multiple intrahepatic pathways, compared to PCOS without HS and obese controls without HS. HS will be related to relative post-prandial hyperglycemia. Post-prandial hyperglycemia will be made worse or remain unchanged with oral contraceptives and better with metformin.

Specific Aims:

Aim 1: In obese girls with PCOS, post-prandial hepatic substrate metabolism will differ by HS status and treatment regimen and can be assessed with just an oral tracer protocol combined with NMR isotopomer analysis.

Hypothesis: Girls with HS will have upregulated post-prandial hepatic non-glycogenic metabolism compared to those without HS. This will be unchanged by oral contraceptives, and decreased with metformin.

Rationale: A marker of whole body DNL was increased in girls with HS, and preliminary work from my K23 project indicates that direct measures of DNL are elevated, but upstream alterations in intrahepatic metabolism are unclear. Oral contraceptives do not mitigate metabolic risk, whereas metformin decreases HS.

Methods: A 6.5 hour OGTT with an oral U-C₁₃glycerol tracer will be paired with NMR isotopomer analysis of serum samples to describe flux through the hepatic pentose phosphate pathway, TCA cycle and DNL pathways in girls with PCOS receiving lifestyle only, metformin or oral contraceptive treatment, and obese girls with regular menses receiving lifestyle therapy.

Aim 2: Describe the optimal timing for identifying metabolomics profiles associated with risk for T2D and HS.

Hypothesis: Metabolomics profiles between girls with HS and worse IR will differ the most between 3-6 hours.

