Likely contributors to above measures: Lipid/glucose markers:(fasting C-peptide and lipid panel, HbA1c); hepatic markers:(c-reactive protein, glucagon, GLP-1 and leptin at baseline, 5 min and 30 min post glucose load to asses change with OG, adiponectin, AST, ALT, GGT), sex-steroids:(DHEAS, free and total testosterone, sex hormone binding globulin, progesterone, estradiol); Body size and composition: (BMI, waist/hip ratio, DEXA, hepatic visceral fat via MRI³⁶⁻³⁹), Whole body fat oxidation at rest and following glucose ingestion as measured with a metabolic cart; Physical activity/ diet:(accelerometer, activity survey (3DPAR); Food frequency survey).Questionnaires for presence of obstructive sleep apnea. Questionnaires for perceived mental strengths and difficulty (note there is no assessment of suicidality on this tool). Obstructive Sleep Apnea, to be assessed with an overnight sleep study via WatchPAT.

B. Description of Population to be Enrolled:

Study staff aims to enroll 20 obese girls with regular menstrual cycles, 20 girls with un-treated PCOS, 20 girls with PCOS treated with at least 6 months of Metformin and 20 girls with PCOS treated with at least 6 months of oral contraceptives. The PCOS groups will be compared to 20 obese non-PCOS controls. This is the number of participants needed to be completed statistically, thus more subjects may be enrolled, to allow for screen failures and dropouts. Total enrollment will be up to 100 participants.

Ethnic Categories	Gender		
	Females	Males	Total
Hispanic or Latino	40	0	40
Not Hispanic or Latino	60	0	60
Ethnic Categories: Total of All Subjects	100	0	100
Racial Categories			
American Indian/Alaska Native	5	0	5
Asian	10	0	10

Native Hawaiian or Other Pacific Islander	10	0	10
Black or African American	32	0	32
White	43	0	43
Racial Categories: Total of All Subjects*	100	0	100

Inclusion Criteria:

- 1) Female
- 2) Ages 12-21
- 3) Sedentary- less than 2.5 hours of moderate (jogging, swimming etc) exercise a week.
- 4) BMI equal or greater than the 90th percentile for age and gender
- 5) For PCOS groups: (NIH definition) irregular menstrual cycles at least 1.5 years after menarche and either clinical evidence of hyperandrogenism or elevated Testosterone (above the norms for age/tanner stage) at time of screening or documented prior to initiation of therapy for OCP and metformin groups.

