- 6) For PCOS groups: patients un-treated or currently treated with either Metformin 1500-2000 mg a day or oral contraception (30-35 mcg ethynodiol a day) for at least 6 months, with > 80% adherence confirmed via refill frequency from pharmacy.
- 7) For non-PCOS groups: regular menstrual cycles at least 1.5 years after menarche and no clinical evidence of hyperandrogenism

Exclusion Criteria:

1. Use of medications known to affect insulin sensitivity: oral glucocorticoids within 10 days, atypical antipsychotics, immunosuppressant agents, HIV medications. Nexplanon, Depo-Provera or Mirena progesterone only contraceptives. Dermal patch or vaginal ring contraception methods. For controls only: metformin or oral contraception.
2. Currently pregnant or breastfeeding women. Development of pregnancy during the study period will necessitate withdrawal from the study.
3. Severe illness requiring hospitalization within 60 days
4. Diabetes, defined as Hemoglobin A1C > 6.4%
5. BMI percentile less than the 90th percentile for age and sex. Weight >325 lbs or <84 lbs.
6. Anemia, defined as Hemoglobin < 10 mg/dL
7. Diagnosed major psychiatric or developmental disorder limiting informed consent
8. Implanted metal devices that are not compatible with MRI
9. Use of blood pressure medications
10. Known liver disease other than NAFLD or AST or ALT >150 mg/mL

Rationale for Inclusion of Non-PCOS Subjects

Obese adolescents are at risk of T2D and its complications, reduced exercise capacity, increased liver and visceral fat, muscle dysfunction and cardiovascular dysfunction therefore the tests

performed screening for each of these problems provide useful information to these subjects. Likewise, sedentary subjects of any weight are at increased risk of reduced bone mineral density (BMD), T2D, reduced exercise capacity, increased liver and visceral fat, muscle dysfunction and cardiovascular dysfunction. Therefore, all of the subjects may benefit from the results of DEXA, glucose testing and exercise prescription and dietary counseling.

C. Study Design and Research Methods

Study Calendar	Visit 1 – Screen	Visit 2 –MRI	Visit 3 – Overnight
Consenting and Eligibility Assessment	X		
History & Physical	X		
Intravenous Blood Draw	X		X
Finger Stick Blood Draw		X	
Urine Pregnancy Test			X
Accelerometer Teaching	X		
Gut Bacteria Collection			X
Questionnaires- SEARCH Food frequency, Activity 3DPAR, Strengths and Difficulties and Sleep assessments			X

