Since the recommendations are not concrete for the 12-17 year old range, we sought to follow what is being done in clinical practice at Children's Hospital Colorado sleep clinics, were a patient to have an inpatient polysomnogram. Sleep studies are read within 5 business days, and we will adhere to this same turnaround timeline. In terms of interpretation, currently, the pediatric guidelines are being applied for the 12-17 year old age group but 2 is considered normal in this age, and thus our post-study for the 12-17 year olds will follow this, and are shown below. Approximately half of the participants have a patient relationship with the PI [name], and thus she can order F/U evaluation if needed, and if not, [name] will request the follow-up be arranged by the primary care provider. We have 2 algorithms by age.

For participants 12-17 years of age:

For participants ≥ 18 years of age:

SUBJECT RECRUITMENT/CONSENT/PAYMENT

1. Subject Recruitment Plan

Subjects will be recruited from pediatric endocrine, PCOS, Lifestyle, adolescent and gynecology clinics, and from the community. We receive 4-8 new PCOS referrals a month, showing the feasibility of recruiting the required subjects. Further, we enrolled >100 obese girls in studies in the last 60 months. The PI and Co-I's have a treatment relationship with girls from clinic or subjects

can call from study advertisements. Protected health information will only be accessible by study investigators. The initial patient contact will be made by personnel who have a treatment relationship with the subject. Our past studies have consented participants and asked if they'd like to be re-contacted for future research studies. Furthermore, after the conclusion of our previous studies in PCOS (this protocol, 14-0542 and 10-1288), participants may have been prescribed treatment with OCP or Metformin, therefore study staff may aim to re-contact them had those participants agreed to be re-contacted and still meet inclusion criteria of the current study.

2. Informed Consent Plan

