A better understanding of how NAFLD develops in girls with PCOS could lead to more effective treatment strategies. This understanding could ameliorate development of diabetes and heart disease for these girls as they become adults, and may also help with many of the health and social difficulties teens with PCOS experience. Since PCOS is one of the most common endocrine diseases in the US female population, improving PCOS care could have major health implications. The data to be generated from this project will be utilized to inform R01 grant applications of treatment trials with new medications. We will also begin to learn the effect of the two existing medical therapies.

Individual: Subjects will benefit from in depth testing for pre-diabetes, fatty liver disease and sleep disorders that are not clinically offered. They will receive extensive counseling for both dietary and exercise lifestyle changes. Similar subjects who completed related protocols (10-1288 and 14-0542) and received this counseling have higher rates of weight loss upon clinical follow-up than those children being seen in obesity clinics alone.

Benefits to participant:

- 1) All subjects will be undergoing measures that can identify insulin resistance, hyperlipidemia, NAFLD or early cardiovascular disease. These measures are not typically done within the scope of daily pediatric practice, and subjects would likely not otherwise know this information. If they have one of these conditions, they will be referred for appropriate follow-up and treatment. If the subjects have signs of obstructive sleep apnea, they will be referred to the sleep clinic for appropriate evaluation and treatment.
- 2) All of the subjects enrolled must be sedentary, with less than 2.5 hours a week of physical activity. This is less than the time recommended by the US Preventive Task Force and the American College of Sports Medicine for this age group. This lifestyle puts them at risk for several diseases including diabetes and cardiac disease later in life, even if they don't have evidence of disease at this time. At the end of the study, all subjects will receive counseling on how to increase their activity levels by trained study staff. Increased activity has been shown to reverse the risk for diseases later in life.

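### The metformin and oral-contraceptive comparisons are worded as drug effects, but the plan compares established adherent users with untreated girls once, so they can support only associations.

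*Combined protocol and SAP*

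**What the plan says.** **Wording.** In section I the Aim 1 hypothesis says of the steatosis-related abnormality: "This will be unchanged by oral contraceptives, and decreased with metformin". The main hypothesis makes a parallel prediction for post-prandial hyperglycaemia. Section III.E, under knowledge to be gained, states: "We will also begin to learn the effect of the two existing medical therapies".

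**Groups.** Section III.B plans "20 girls with PCOS treated with at least 6 months of Metformin", a matching oral-contraceptive group and 20 untreated girls with PCOS. Inclusion criterion 6 admits "patients un-treated or currently treated with either Metformin 1500-2000 mg a day or oral contraception" and requires at least 6 months of treatment and over 80% adherence by pharmacy refill. For treated girls, criterion 5 allows the androgen evidence to be "documented prior to initiation of therapy for OCP and metformin groups".

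**Measurement.** The study calendar in section III.C has one screening visit, one MRI visit and one overnight visit. The tracer OGTT takes place once, at Visit 3.

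**Analysis.** Section VII, secondary aim b), says "we will compare the untreated group to the treatments individually". Stated adjustments are sleep apnoea for all measures, ethnicity if the groups differ, and activity and sleep for the OGTT indices. Weight and BMI adjustment is judged unnecessary because flux is expressed per kg of fat-free mass.

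**Recruitment.** The recruitment plan notes that, after this protocol, 14-0542 or 10-1288, "participants may have been prescribed treatment with OCP or Metformin, therefore study staff may aim to re-contact them". Section III.E says that girls who completed the two related protocols and "received this counseling have higher rates of weight loss upon clinical follow-up" than children seen in obesity clinics alone.

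**The concern.** To say that a drug decreases an abnormality or leaves it unchanged is to compare the same girl, or exchangeable girls, with and without the drug. Here a prescriber decided who was treated, and only girls who stayed on treatment and refilled it can enter. Untreated girls pass no such filter.

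Lower flux on metformin could therefore reflect milder disease or the habits that go with adherence. Similar flux could mean that metformin went to girls with worse livers and brought them down to the untreated average. The same holds for oral contraceptives. These biases point in different directions, and a larger sample removes none of them.

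Section III.E says the data will inform grant applications for treatment trials, so a difference misread as a drug effect would carry forward into their planning.

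**Working it through.** **1. The plan's own power figure.** Section VII, secondary aim b): difference 2, SD 2 (µmol/min/kg FFM), 30 untreated versus 15 treated, alpha 0.05, stated power 0.87.

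- Standard error = 2 × √(1/30 + 1/15) = 0.632; noncentrality = 2 / 0.632 = 3.16.
- Two-sided t test on 43 degrees of freedom: power 0.871. The stated figure reproduces.
- With the 20 and 20 of section III.B, the standard error is 2 × √(1/20 + 1/20) = 0.632 and power is 0.869. The mismatch in group sizes does not matter for this point.

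The arithmetic is sound. The problem is what the difference means.

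**2. What each safeguard covers.**

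| Source of difference between treated and untreated girls | Covered in the plan? |
|---|---|
| Sleep apnoea | Yes, all measures |
| Ethnicity | Yes, if groups differ |
| Current activity, sleep | For the OGTT indices, with and without |
| Reason for prescription | No |
| Pre-treatment steatosis or metabolic severity | No; steatosis matching is stated only for PCOS versus controls |
| Persistence and adherence | Required of treated girls only |
| Earlier study participation and counselling | No |

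The limitations in section IV cover method development, recruitment and drop-out. Non-random treatment is not among them.

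**3. Illustration of size.** The documents give no pre-treatment steatosis prevalence by treatment group, so the imbalance is my assumption. The 3-unit steatosis difference is the plan's, from section VII.

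- Shift = imbalance in prevalence × 3.
- 20 points: 0.20 × 3 = 0.6 units; 0.6 / 2 = 30% of the effect sought.
- 30 points: 0.30 × 3 = 0.9 units; 0.9 / 2 = 45%.

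**4. Consequence of such a shift** (two-sided t test, SD 2, 20 versus 20; 30 versus 15 agrees to within 0.3 percentage points):

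| Situation | Observed mean difference | Chance of significance |
|---|---|---|
| No drug effect, no imbalance | 0 | 5% |
| No drug effect, shift 0.6 | 0.6 | 15% |
| No drug effect, shift 0.9 | 0.9 | 28% |
| True effect 2, no imbalance | 2 | 87% |
| True effect 2, opposing shift 0.6 | 1.4 | 58% |
| True effect 2, opposing shift 0.9 | 1.1 | 40% |

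The error can go either way: a drug effect claimed where there is none, or a real one missed.

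**The case against.** **The causal reading can be overdone.** The statement of Aim 1 says only that metabolism will differ by regimen, and its methods describe flux in each group. Section VII makes steatosis versus no steatosis in untreated PCOS the primary comparison. Section III.E claims only a beginning of knowledge about the drugs. This stands. It confines the fault to the hypotheses and the knowledge statement, but those are the sentences against which the results will be read.

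**Counselling.** A reader might infer that earlier study counselling has already distorted the treated groups. The documents do not support that. Re-contact is only a possibility, and no share is given. Re-contacted girls must still meet the BMI and inactivity criteria, which limits how far strong responders to counselling can enter. Untreated girls may be earlier participants too. The background statement that weight loss reverses fatty liver concerns obese youth without PCOS. Counselling is therefore a possible further difference, not an established one.

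**The size is assumed.** This also stands. Section II puts fatty liver at 50-70% in obese women with PCOS and 20-30% without, a gap of at least 20 points (50 − 30). The assumed imbalance within PCOS is as large as the lower part of that whole gap. The 3-unit figure comes from 13 men without and 6 with steatosis under hyperinsulinaemia. The 15 and 15 split in section VII would set the untreated steatosis share near one half by recruitment, but it does nothing for the treated groups.

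**Adjustment may not rescue the comparison.** Criterion 5 accepts clinical evidence alone, and section III.C notes that referring physicians often leave the work-up incomplete, so pre-treatment laboratory values may be missing. In the preliminary sleep data, BMI percentile barely separates the groups (98 versus 97) while liver fat is 10.5 versus 5.3. Several added covariates with about 20 girls per group is a poor trade. This is why rewording comes first and any adjustment is only exploratory.

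**Conclusion.** The point holds as a limit on what may be concluded. The treatment hypotheses in section I and the knowledge statement in section III.E claim effects. The design gives one unpaired comparison of untreated girls with girls already prescribed, and adhering to, a drug for at least 6 months. Without allocation, a pre-treatment outcome or adjustment for reason for prescription, a difference or its absence cannot be attributed to the drug.

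The direction and size of the bias are unknown. The 0.6 to 0.9 units (30-45% of the sought effect) rest on an assumed 20 to 30 point imbalance and the plan's borrowed 3-unit difference. They show that a plausible selection effect could matter; they do not estimate one. The primary steatosis comparison within untreated PCOS does not depend on this point.

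**What to change.** 1. **Reword.** In section I (main and Aim 1 hypotheses) and section III.E, present the treatment results as associations. For example: among girls with PCOS measured once, post-prandial non-glycogenic hepatic metabolism will be lower in established adherent metformin users than in untreated girls, and similar in established adherent oral-contraceptive users. Add to section IV that treatment was not allocated, that no pre-treatment outcome exists, and that treated girls were selected on persistence and adherence.
2. **Record earlier participation.** In all groups, note participation in 10-1288, 14-0542 or this protocol. Repeat the treated-versus-untreated comparisons without those girls. This protocol belongs on the list because the recruitment plan names it as a source, so one girl could appear both untreated and treated.
3. **Describe comparability.** Where pre-treatment ALT/AST, HbA1c and BMI already exist in the records, abstract them and tabulate them by group, beside screening values for untreated girls. Label any adjustment for them exploratory. Do not adjust the treatment comparison for current steatosis: the Aim 1 rationale says metformin lowers it, so adjustment could remove part of the drug's own association.

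**Cost.** Text changes, one data field, a limited chart abstraction and one sensitivity analysis; no new visit or participant. The claim becomes more modest and some pre-treatment values will be missing. The sensitivity analysis is smaller: if exclusions left 15 in one group against 20 in the other, power for a difference of 2 with SD 2 would be 0.81.
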